A comparison of four different treatment regimens as the  
first-line treatment of Helicobacter pylori in Chinese children  
and investigation of resistance -a multicenter study

2017.10.1

With the resistance of *Helicobacter pylori* increasing, low and unsatisfactory eradication rate (64%) have been observed with standard triple therapy in European children. Which regimen is appropriate for Chinese children? There is no large scale, multi center studies in China about treatment, CYP2C19 gene polymorphism, resistance rate and resistance genotype. We want to perform a research to compare three different treatment regimens ( triple therapy, sequential therapy, bismuth quadruple therapy and concomitant therapy) as the first-line treatment of *Helicobacter pylori* in Chinese children and investigation of resistance and impact factors. The results of the study will provide theoretical basis to make the new guideline of diagnosis and therapy of *Helicobacter pylori* in Chinese children. It advance instruct and norm the clinical practice for Chinese pediatrician to increase the cure rate of *Helicobacter pylori* and decrease the resistance. To identify factors that influence efficacy of the regimens.

This is a prospective, multicenter,open-label, randomized controlled trial. Based upon published data, we assumed that Hp eradication rate would be 67.7% with standard therapy, 81.4% with sequential therapy, 91.9% with bismuth quadruple therapy and 91.2% with concomitant therapy. Based on a statistical power of 0.9 to detect a significant difference( $P<0.05$ ), 69 patients were required for each group in one center. In consideration of up to 15% subject loss of follow-up, at least 1440 patients total were required.

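### Does a 0.7-point assumed gap between bismuth quadruple and concomitant therapy leave the trial unable to answer its question?

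*Protocol*

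**What the plan says.** The opening summary of the protocol notes a low eradication rate with triple therapy in European children and then asks "Which regimen is appropriate for Chinese children". The results are meant to support a new Chinese paediatric guideline.

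The sample-size paragraph in the same summary gives the planning rates: "we assumed that Hp eradication rate would be 67.7% with standard therapy", "81.4% with sequential therapy" and "91.9% with bismuth quadruple therapy and 91.2% with concomitant therapy". The size rests on one statement, "Based on a statistical power of 0.9 to detect a significant difference", at P<0.05. From this it concludes that "69 patients were required for each group in one center". With the allowance "In consideration of up to 15% subject loss of follow-up", it states that "at least 1440 patients total were required".

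The text after the Exclusion Criteria randomises children to the four regimens. It makes eradication at 4–6 weeks after treatment the primary outcome and lists side effects, impact factors and microbiome changes as secondary outcomes.

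The protocol does not name the pair to which the power refers. It contains no statement that all four regimens will be ranked, or that the two best will be separated.

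**The concern.** The trial has four arms and one power statement, and the two arms expected to do best are assumed to differ by 91.9 − 91.2 = 0.7 points. If the 0.9 power is read as covering every pair, the planning rates contradict it for this one: no feasible trial would detect 0.7 points.

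If triple and sequential therapy are beaten as expected, the choice left for a guideline lies between these two. The likely result there is a non-significant difference. A reader might wrongly take that as proof of equal efficacy, or might prefer whichever arm has the higher point estimate. The protocol gives no non-inferiority margin that would allow a firmer statement.

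**Working it through.** **Inputs.** The four rates, power 0.90, P<0.05, 69 per group, 15% loss and the total of 1440 all come from the sample-size paragraph. Three things are assumed because the protocol does not state them: a two-sided test, equal allocation, and analysis of all centres together.

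**1. Which comparison gives 69?** For two proportions with pooled variance under the null,

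n = [1.96·√(2p̄(1−p̄)) + 1.2816·√(p₁(1−p₁)+p₂(1−p₂))]² / d².

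For triple (0.677) versus concomitant (0.912), p̄ = 0.7945 and d = 0.235:

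- 1.96 × 0.5714 = 1.1200, and 1.2816 × 0.5467 = 0.7007
- n = (1.8207)² / 0.0552 = 60.0
- with continuity correction, (n/4)·[1+√(1+4/(n·d))]² = 68.3, rounded up to **69**

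This matches the stated figure. The other five pairs, one- and two-sided, with and without the correction, do not give 69; nor do the unpooled or arcsine versions. Triple versus bismuth gives 64 with the correction. A four-group chi-square test needs 53. The stated size therefore fits a comparison of a new regimen with standard therapy, not one between the two leading regimens.

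**2. Evaluable children per group.** 1440 / 4 = 360, and 360 × 0.85 = 306.

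**3. Bismuth versus concomitant.**

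- n for 90% power: (1.96 × 0.39334 + 1.2816 × 0.39331)² / 0.007² = 33,176 per group
- standard error at 306: √[(0.919×0.081 + 0.912×0.088)/306] = 0.0225
- 95% CI half-width: 1.96 × 0.0225 = 0.044, or 4.4 points
- chance of a significant result: about 5.0% in the expected direction plus 1.2% in the other, 6.1% in all before rounding

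These figures assume that the true rates equal the planning rates. At 306 per group, a true rate 7.3 points below 91.9% would be detected with 80% power, and one 8.6 points below with 90%.

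**4. All six pairs at 306 per group, two-sided 0.05.** Bonferroni power (0.05/6) is shown as a stress test; the protocol mentions no adjustment.

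| Pair | Assumed gap (points) | Power, unadjusted | Power at 0.05/6 |
|---|---|---|---|
| Triple vs sequential | 13.7 | 97.5% | 89.8% |
| Triple vs bismuth | 24.2 | about 100% | about 100% |
| Triple vs concomitant | 23.5 | about 100% | about 100% |
| Sequential vs bismuth | 10.5 | 97.0% | 88.4% |
| Sequential vs concomitant | 9.8 | 94.3% | 81.5% |
| Bismuth vs concomitant | 0.7 | 5.0% | 1.0% |

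The one pair without power is the one the planning rates treat as practically equal.

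**5. Does the text claim power for that pair?** The power statement speaks of one difference and names no pair. The question about the appropriate regimen follows directly on the poor result of triple therapy in Europe, so it asks what should be used in view of that result. Showing that two regimens both beat triple and sequential therapy answers it. The listed secondary outcomes, side effects among them, also give a basis for weighing two regimens with similar eradication.

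**The case for a change.** The strongest case for the concern is that the power statement stands alone for a four-arm trial and excludes no pair. A reader may take it to cover all six. For one pair the protocol's own rates contradict that reading, and it is the pair a guideline panel would face last. The remedy would be cheap: say that the 0.9 does not apply there, report the difference with its confidence interval, and state that non-significance is not equivalence. Any margin would have to be fixed before results are known to be credible.

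Some of this stands. The arithmetic is right, the paragraph does not name its comparison, and a non-significant result between these arms would not show equal efficacy. With a half-width of 4.4 points, it would remain compatible with a true gap of several points.

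It does not make the plan wrong. The all-pairs reading is supplied by the reader; the 69 per group points to a comparison with standard therapy. Correcting the statement for this pair would disclaim something the protocol does not assert. The interval and the reporting sentence belong in a statistical analysis plan, which may exist but is not at hand. A non-inferiority aim would be a different design choice. Its size depends wholly on a margin nobody has set: by way of illustration, 188 per group for 10 points and 880 for 5 points, at one-sided 0.025 and 90% power.

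**Conclusion.** The concern does not hold. It is true that bismuth versus concomitant has about a 6% chance of significance at 306 per group, and that 33,176 per group would be needed for 90% power. But no stated figure or aim depends on separating these two arms. The 69 per group is reproduced by triple versus concomitant therapy. The total of 1440 gives 94.3% to about 100% unadjusted power for the other five pairs, and 81.5% or more even at 0.05/6. A sponsor following the text could soundly conclude that both leading regimens beat triple and sequential therapy.

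This rests on two-sided testing, equal allocation, 15% loss, pooling of centres, and the planning rates being near the truth. If the two leading regimens really differ by 7 to 9 points, the trial has a good chance of showing it. What remains is a matter of how the result for this pair is reported, not an error in the protocol.

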#### Exclusion Criteria:

Patients were excluded if they had taken proton pump inhibitors, H2-receptor antagonists or antibiotics in the 4 weeks prior to the study. Patients with known antibiotic allergy,hepatic impairment or kidney failure were also excluded. Patients who received Hp therapy before were also excluded.

Eligible children were randomly divided into four groups: standard triple therapy, sequential therapy, bismuth quadruple therapy and concomitant therapy. The course of

treatment is 14 days. The primary outcome measure was the Hp eradication rate at 4-6 weeks after completion of treatment which was confirmed by a negative of 13 UBT. Secondary outcome measures included side effects, impact factor and changes of microbiome after the therapy.

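### The total of 1440 does not follow from 69 per group in one centre, 15% loss and four groups; with the number of centres unstated, the direction of the error is unknown

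*Protocol*

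**What the plan says.** The sample-size paragraph in the protocol's opening section assumes eradication rates of "67.7% with standard therapy, 81.4% with sequential therapy, 91.9% with bismuth quadruple therapy and 91.2% with concomitant therapy". At a power of 0.9 and P<0.05 it concludes that "69 patients were required for each group in one center". The next sentence gives the total: "In consideration of up to 15% subject loss of follow-up, at least 1440 patients total were required". The multiplication is not shown, and the number of centres appears nowhere; the trial is described only as multicentre.

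The number of groups is not consistent. The title announces "A comparison of four different treatment regimens", and the randomisation paragraph under Exclusion Criteria says "Eligible children were randomly divided into four groups". The aim sentence in the background paragraph says the study will "compare three different treatment regimens" and then lists four.

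**The concern.** The total is presented as the result of three inputs: a size per group in one centre, a 15% loss allowance and the number of groups. The only missing factor is the number of centres, so 1440 should be a whole multiple of the inflated per-centre size. It is not.

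The figure is the minimum enrolment. If it does not follow from its basis, a reader cannot tell whether the trial recruits more or fewer patients than its own per-centre requirement, or which of the stated inputs is wrong. The word three in the aim sentence raises the further possibility that the total was computed for a different number of groups.

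**Working it through.** **Inputs from the protocol.** 69 per group in one centre; loss up to 15%; four groups; total at least 1440; the four assumed rates. **Assumptions.** Equal allocation and equal centres, since one figure is given for every group; two-sided testing, since sidedness is not stated. The number of centres is left open.

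**1. Reproducing the 69.** Take standard (0.677) against concomitant (0.912), two-sided 0.05, power 0.90. The mean rate is 0.7945 and the difference 0.235.
- n = [1.960 x sqrt(2 x 0.7945 x 0.2055) + 1.282 x sqrt(0.677 x 0.323 + 0.912 x 0.088)]² / 0.235² = 60.0
- With continuity correction: (60.0/4) x [1 + sqrt(1 + 4/(60.0 x 0.235))]² = 68.3, rounded up to 69.

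So 69 reproduces, and the break lies in the step from 69 to 1440.

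**2. Inflating for 15% loss.**
- Multiplying: 69 x 1.15 = 79.35, rounded up to 80.
- Dividing: 69/0.85 = 81.18, rounded up to 82. This is the form that leaves 69 after 15% loss.

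**3. Total for four groups** (320 or 328 per centre).

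| Centres | 80 x 4 x centres | 82 x 4 x centres | Stated 1440 is |
|---|---|---|---|
| 4 | 1280 | 1312 | 128 to 160 above |
| 5 | 1600 | 1640 | 160 to 200 below |
| 6 | 1920 | 1968 | 480 to 528 below |

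Working backwards, 1440/320 = 4.50 centres and 1440/328 = 4.39. Without rounding the per-group figure, the results are 4.54 and 4.43. With no loss allowance, 1440/276 = 5.22. None is whole.

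**4. What 1440 delivers against the 69** (360 per group).

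| Centres | Enrolled per group per centre | Evaluable after 15% loss | Loss that would leave 69 |
|---|---|---|---|
| 4 | 90 | 76.5 | 1 - 69/90 = 23.3% |
| 5 | 72 | 61.2 | 1 - 69/72 = 4.2% |
| 6 | 60 | 51 | none: already below 69 |

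**5. Other group counts.** With the same two loss formulas, taken unrounded, rounded up or rounded to nearest, for two to four groups and 1 to 24 centres, the only exact matches are 80 x 3 x 6 = 1440 and 80 x 2 x 9 = 1440. The second has no support in the text. The first fits the word three in the aim sentence, but it needs six centres, which are not stated, and the multiplying formula; dividing gives 82 x 3 x 6 = 1476.

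**6. Pooled power at 1440.** 360 x 0.85 = 306 evaluable per group. The test is two-sided, without continuity correction.

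For sequential (0.814) against concomitant (0.912), the null standard error is sqrt(2 x 0.863 x 0.137/306) = 0.0278, and under the alternative it is sqrt((0.814 x 0.186 + 0.912 x 0.088)/306) = 0.0275. At unadjusted 0.05, (0.098 - 1.960 x 0.0278)/0.0275 = 1.58, a power of 0.943. At 0.05/6 the critical value is 2.638, and the power is 0.81.

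| Pair | Power at 0.05 | Power at 0.05/6 |
|---|---|---|
| Standard v sequential | 0.975 | 0.90 |
| Sequential v bismuth | 0.970 | 0.88 |
| Sequential v concomitant | 0.943 | 0.81 |
| Standard v bismuth, standard v concomitant | >0.99 | >0.99 |
| Bismuth v concomitant | about 0.06 | lower still |

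**The case against.** The strongest reply is that the total is a floor and the loss rate a ceiling. With four centres, 1440 gives 90 enrolled and 76.5 evaluable per group per centre, above 69, and with fewer centres the margin is larger. This stands. A reader might infer that the per-centre requirement and the total cannot both hold for four groups; the document does not support that, because they conflict only from five centres upward. What fails for every number of centres is the derivation: 1440 is not the number that the stated basis yields.

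An exact four-group route also exists if rounding is loose: 81.2 taken up to the next ten is 90, and 90 x 4 x 4 = 1440. The protocol states no such rounding, and 90 is a 23.3% allowance for 69 rather than 15%. It does show that 80 x 3 x 6 is not the only possible origin.

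A reader might also infer that the total is proven to be left over from a three-group design and is therefore 480 or more patients short. That goes too far. Six centres appear nowhere, 1440 has many factorisations, the same paragraph assumes four rates, and the 69 itself reproduces from the last-listed regimen. The word three may be a simple slip.

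Finally, a reader might conclude that the trial is underpowered. Pooled over centres it is not, apart from bismuth versus concomitant, where the assumed rates differ by only 0.7 percentage points.

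**Conclusion.** The point holds as a fault in the derivation of a stated sample size, and it should be fixed. Under the usual loss formulas, 69 per group in one centre with 15% loss and four groups does not give 1440 for any whole number of centres. Relative to the protocol's own basis, the total is 128 to 160 above the minimum with four centres, 160 to 200 below it with five and 480 to 528 below it with six. Because the number of centres is not stated, neither the direction nor the size can be settled from the document.

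The contradiction between three and four regimens is plain on the page and does not depend on any explanation of 1440. The shortfalls per centre rest on equal groups and equal centres; the pooled power rests on equal groups, the assumed rates and two-sided testing. No statistical analysis plan is at hand, but a later plan would not make these protocol figures agree with one another.

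**What to change.** Change three to four in the aim sentence. Then choose one basis for the total.

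- **Per-centre basis.** State the number of centres and restate the total as 82 x 4 x centres: 1312 for four, 1640 for five, 1968 for six. Against 1440 this means 128 fewer patients with four centres, 200 more with five or 528 more with six.
- **Pooled basis.** Keep 1440, remove the 69 per group in one centre as its justification, and write, for example: *Assuming equal allocation, 1440 children (360 per group, 306 evaluable after 15% loss) give at least 94% power at an unadjusted two-sided 0.05 for every pair at the assumed rates except bismuth versus concomitant (about 6%), which is not powered for a difference. With a Bonferroni correction over six pairs, power for sequential versus concomitant falls to about 81%.* This costs wording only and adds no patients.

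The pooled basis is the simpler repair if 1440 is the intended enrolment. Whichever is chosen, the calculation leading to the total should be shown.

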#### Inclusion Criteria:

Children 6-18 years of age who were referred for upper endoscopy and confirmed to have Hp infection

#### Exclusion Criteria:

Patients were excluded if they had taken proton pump inhibitors, H2-receptor antagonists or antibiotics in the 4 weeks prior to the study. Patients with known antibiotic allergy,hepatic impairment or kidney failure were also excluded. Patients who received Hp therapy before were also excluded.

Eligible children were randomly divided into four groups: standard triple therapy, sequential therapy, bismuth quadruple therapy and concomitant therapy. The course of

treatment is 14 days. The primary outcome measure was the Hp eradication rate at 4-6 weeks after completion of treatment which was confirmed by a negative of 13 UBT. Secondary outcome measures included side effects, impact factor and changes of microbiome after the therapy.

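### Should the plan require a drug-free interval before the breath test that defines eradication?

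*Protocol*

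**What the plan says.** The paragraph on groups and outcomes, printed under Exclusion Criteria in the Protocol, defines the primary outcome as "the Hp eradication rate at 4-6 weeks after completion of treatment which was confirmed by a negative of 13 UBT". It attaches no other condition to the test and goes straight on to the secondary outcomes: "Secondary outcome measures included side effects, impact factor and changes of microbiome after the therapy".

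The same section does restrict drugs at entry: "Patients were excluded if they had taken proton pump inhibitors, H2-receptor antagonists or antibiotics in the 4 weeks prior to the study".

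The opening design paragraph describes the conduct: "This is a prospective, multicenter,open-label, randomized controlled trial". It gives the assumed eradication rates as "67.7% with standard therapy, 81.4% with sequential therapy, 91.9% with bismuth quadruple therapy and 91.2% with concomitant therapy" and the total as follows: "In consideration of up to 15% subject loss of follow-up, at least 1440 patients total were required".

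**The concern.** Entry and outcome are treated differently. A child must be free of three drug classes for four weeks to join, but nothing is said about the same classes before the test that decides success. The 4-6 week gap separates the test from the study drugs only. A child given an unrelated antibiotic or acid suppressant in week 3 still meets the outcome definition, and a negative result would count as cure.

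If such a drug can hide a persisting infection, the error runs one way: only children who are still infected can be misread, so each arm's rate can only go up. Arms with more failures gain most, which narrows the differences. In an open-label trial, drug use after treatment could also differ by arm, and a comparison could then move in either direction. The results are meant to inform a guideline, so the absolute rates matter as well as the order of the arms.

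**Working it through.** **Inputs from the Protocol.** Assumed rates p: triple 67.7%, sequential 81.4%, bismuth quadruple 91.9%, concomitant 91.2%. Power 0.9, significance level 0.05, 69 per group in one center, total 1,440, loss 15%.

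**Assumptions not in the Protocol.** Two-sided test; equal allocation; f, the share of still-infected children whose test is negative because of a non-study drug, taken as 2% to 12%; share of children using such drugs, taken as 10% to 30%.

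**1. The plan's own figure.** Triple against concomitant (67.7% against 91.2%), two-sided 5%, 90% power: the two-proportion formula gives 61 per group, and 69 with continuity correction. The stated 69 is reproduced. The present point does not depend on it.

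**2. Equal f in all arms.** Observed rate = p + (1 - p) × f, so every difference is multiplied by (1 - f).

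| | f = 0 | f = 2% | f = 12% |
|---|---|---|---|
| Triple | 67.7 | 68.35 | 71.58 |
| Sequential | 81.4 | 81.77 | 83.63 |
| Bismuth quadruple | 91.9 | 92.06 | 92.87 |
| Concomitant | 91.2 | 91.38 | 92.26 |
| Sequential minus triple | 13.7 | 13.43 | 12.06 |
| Bismuth minus triple | 24.2 | 23.72 | 21.30 |

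Example: triple at f = 12% is 67.7 + 32.3 × 0.12 = 71.58. The order of the arms cannot change.

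**3. Power.** Evaluable per arm = 1,440 × 0.85 / 4 = 306. For sequential against triple, power is 97.5% at f = 0, 97.1% at 2% and 94.9% at 12%. This is pooled over centers. The Protocol's 90% belongs to 69 per group in one center, so the two should not be set against each other as if on one basis.

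**4. Unequal f, at the extreme of the assumed range (12% in one arm, 0% in the other).**
- Triple only: sequential minus triple = 81.40 - 71.58 = 9.82 points, power 81.9%; bismuth minus triple = 91.90 - 71.58 = 20.32.
- Sequential only: sequential minus triple = 83.63 - 67.70 = 15.93.
- Bismuth only: bismuth minus triple = 92.87 - 67.70 = 25.17.

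**5. Bismuth against concomitant.** These are 0.7 points apart and would swap if f in concomitant alone reached 0.7 / 8.8 = 8%. That is about 2 children: 306 × 0.088 = 27 failures, and 8% of 27 is about 2. The 95% half-width for this difference is 1.96 × √[(0.919 × 0.081 + 0.912 × 0.088) / 306] = 4.4 points. The trial cannot order these two arms whether or not any test is masked.

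**6. What a rule would cost.** Applying the four-week interval to the outcome test means testing no earlier than four weeks after last use. Last use by week 2 still allows a test by week 6; last use in week 4 means week 8. With 10% to 30% use, 122 to 367 of 1,440 × 0.85 = 1,224 tests are affected. If last use is spread evenly over weeks 0 to 4 and tests are planned for week 4, half of them, 61 to 184, fall after week 6.

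**The case for a change.** The best case for a change is that the timing of a test, and what is recorded before it, are matters of conduct. An analysis plan cannot recover drug exposure that was never collected. The children were referred for endoscopy, so later use of acid suppressants is plausible. Asking about it costs little, and in the worst case above the power for sequential against triple falls to about 82%.

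Part of this stands. The text does treat entry and outcome differently, the 4-6 week gap does not cover non-study drugs, and a pre-test condition would normally sit in a protocol. If masking occurs, the direction of the error in each arm's rate is clear.

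The rest is weaker. The entry restriction carries no stated reason and is not tied to a breath test: children enter after referral for endoscopy with confirmed infection, and the method of confirmation is not named. Since the trial also studies resistance, the entry interval may serve that purpose, and the asymmetry is not a contradiction. Nor does a short outline that is silent on recording show that case report forms omit these drugs. The 82% needs 12% masking in one arm and none in the other, and nothing in the documents supports that pattern.

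**Conclusion.** No change to the plan follows. This is a detail that a brief protocol leaves unwritten, not a mistake in what it states. Whether there is any bias depends on three things the documents do not give: that such drugs mask infection on this test, how often they are used, and how large f is.

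Under equal f of up to 12%, the overstatement is at most 3.9 points, in the triple arm. The order of the arms holds, and sequential against triple keeps about 95% power with 306 evaluable per arm (equal allocation assumed). Only a strongly unequal f would matter more, and bismuth minus triple would still be at least 20.3 points.

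A binding rule is not a clear gain. It would move an assumed 61 to 184 tests out of the primary window. If drug use differed by arm, the timing of the test would differ by arm too. It would also raise the question of how to count a child who never meets the interval. Where drug use before the test has been recorded, analysts can keep the primary analysis on the result as obtained and check it by setting aside the affected tests, positive and negative alike.
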